### **Other Questionnaires**

Comparison of the total score of the frequency and the total score of the severity of symptoms evaluated in the Vocal Tract Discomfort (VTD) scale pre- and post-treatment will be compared using paired sample  $t$ -tests. The comparison of the frequency and the severity of particular symptoms of the VTD scale pre- and post-treatment will be made by means of the non-parametric Mann – Whitney  $U$  test. Comparison of the frequency and the intensity of particular VTD items in the respective subgroups of patients pre- and post-treatment using ANOVA. Finally, the relationships between the results of the VTD scale and VHI and MPT will be estimated by means of the Pearson  $r$  coefficient. Other non-validated questionnaires will be reported using descriptive statistics.

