## 5. STUDY DESIGN AND METHODS OF DATA COLLECTION AND STATISTICAL ANALYSIS PLAN

The aim of this proof-of-concept study is to evaluate whether the approach used in the Complete Vocal Technique to improve voice production in singers and performers can be applied to patients with Type I-III Muscle Tension Dysphonia pattern using a Telehealth medium. Ten consecutive patients seen in an NHS Joint SLT/ENT Voice clinic who meet the inclusion/exclusion criteria and who give consent will be invited to take part in the study. In addition, MTD patients awaiting SLT-VT will be invited to take part in the study. Data including validated patient self-assessment questionnaires, audio-perceptual evaluation of the voice, acoustic and EGG recordings of the voice and an aerodynamic measure (MPT), will be collected after recruitment in a research clinic at the beginning of the study (t=0) and again at the end of the study (t=8). Data will be collected by the study Laryngologist or study SLT. Additional questionnaires will also be given to patients and Therapists at the end of the study to obtain feedback on satisfaction with achievement of goals, the therapy, and the use of Teletherapy to deliver the treatment. Quantitative standard descriptive and inferential statistics methods will be applied to compare pre-and post-therapy measures using the VHI as the primary outcome measure as well as the selected secondary outcome measures.

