### VHI

Paired-samples t tests will be applied to the pre-treatment and post-treatment primary outcome measure scores (total VHI score).

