### Acoustic, EGG and MPT measures

Paired-samples t tests will also be applied to the secondary acoustic outcome measures (EGG, acoustic and MPT measures), together with 95% confidence intervals.

To control for Type 1 error of the primary outcome and secondary outcome analyses while maintaining an acceptable level of statistical power, the alpha level for all t-test comparisons will also be assessed at .025. Treatment effects will be assessed by comparing the pre-treatment to post-treatment change ( $\Delta$ ) scores, plotted as a forest plot in order to display the average  $\Delta$  change for each outcome measure and corresponding 95% confidence interval. Any significant treatment effects will be followed up with calculations of effect size using Cohen's d.

SHORT TITLE/ACRONYM: CVT4MTD

IRAS:306954

Measurement reliability for acoustic analyses will be calculated by reanalysis of 10% of the recordings. The recordings chosen for reliability analysis will be randomly selected from the total number of recordings. Pearson product–moment correlations will be used to assess inter-measurer and intra-measurer reliability of the acoustic and EGG measurements.

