### **CAPE-V**

For the secondary outcome measure CAPE-V, three experienced judges will be asked to rate all voice samples using the first four dimensions (overall severity, roughness, breathiness, and strain; on 100-mm visual analog scales (VAS) (Kempster et al, 2009). The judges will be blinded to pre- and post-treatment status of the voice samples. The voice samples will be presented in random order. The rating forms will be scored, and then scores for each subject will be averaged across the three judges. Average scores will be used for group analyses. Interrater agreement will be assessed using procedures described by Kreiman and Gerratt (1998). Agreement equivalent to within 1 point on a 7-point Equal Appearing Interval (EAI) scale will be calculated for each possible pair of raters for each voice sample. On a 100-mm visual analog scale, scores that fall within 7.2 mm will be considered to be in exact agreement on a 7-point EAI, and scores that are within 21.5 mm (7.2 + 14.3 mm) will be considered to be within 1 scale value. Two scores will be considered to agree if they fall within  $\pm 21.5$  mm on the VAS (probability of chance agreement  $p = 0.39$ ). The probability of agreement will be calculated by totaling all pairs of scores that agree and dividing by the total number of score pairs. Twenty percent of the voice samples will be randomly selected to be repeated for each judge. Repeat ratings will be used to assess intra-rater agreement, using the same calculation. To test for differences in the four CAPE-V dimensions, a multivariate analysis of variance will be applied to the pre-treatment to post-treatment change ( $\Delta$ ). Paired-samples  $t$  tests will also be applied to pre-treatment to post-treatment changes for each of the four dimensions within each group. A multiple comparison adjustment will be made for the four comparisons using the Bonferroni multiple-comparison procedure. The confidence intervals will be similarly adjusted for four comparisons, so the reported 95% confidence interval (CI) will actually be a 98.75% CI, which is a Bonferroni-adjusted CI.

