## 7.2. Sampling

The paper questionnaires and forms will be completed by patients during the attendance at the research clinic at (t=0) and (t=8) and administered by the study Laryngologist and SLT-VT and form part of the Case Report Form (CRF). The acoustic and EGG voice recordings will also be made at these research clinic appointments by a member of the study team. CRFs and study documentation will be stored in a locked cabinet in a locked ENT department room. Questionnaire and other form data will be transcribed onto a digital platform and kept in patient folders in a secure Network storage area and a copy of relevant clinical data will also form part of the patient's digital health record (DHR). Acoustic and EGG data will be similarly stored with print outs of summary statistics forming part of the patient's DHR and CRF.

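### Individual VTD symptoms, scored twice by the same patients, are compared with the Mann-Whitney U test, which assumes independent samples

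*Combined protocol and SAP*

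**What the plan says.** The VTD scale is a patient self-report, listed as secondary outcome 4c in section 4.2. Its analysis is in section 5, Other Questionnaires:

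- **Totals:** the total frequency and total severity scores "evaluated in the Vocal Tract Discomfort (VTD) scale pre- and post-treatment will be compared using paired sample" t-tests.
- **Individual symptoms:** the very next sentence says the comparison of the frequency and severity of "particular symptoms of the VTD scale pre- and post-treatment will be made by means of the non-parametric Mann – Whitney" U test.

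Both sets of scores come from the same people. Section 5 describes one cohort of ten, with data collected "at the beginning of the study (t=0) and again at the end of the study (t=8". Section 7.2 adds: "The paper questionnaires and forms will be completed by patients during the attendance at the research clinic at (t=0) and (t=8". No control arm or unlinked sample is described.

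The other pre/post analyses work within patient:

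- **VHI:** "Paired-samples t tests will be applied to the pre-treatment and post-treatment primary outcome measure scores".
- **Acoustic, EGG and MPT measures:** "Paired-samples t tests will also be applied to the secondary acoustic outcome measures".
- **CAPE-V:** paired t "tests will also be applied to pre-treatment to post-treatment changes for each of the four dimensions", plus a multivariate analysis of the change scores.

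On significance level, the plan says "the alpha level for all t-test comparisons will also be assessed at .025". That covers t-tests, so no level is set for the rank test.

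**The concern.** The Mann-Whitney test would treat the 20 scores for an item as coming from 20 different people. Its null distribution has no term for the link between a patient's two scores, so its p-value is not valid for this design. Preferring a rank test for ordinal items is reasonable. It does not explain dropping the pairing, because a paired rank test exists.

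What is at stake is the item-level reading of one secondary outcome. Secondary objective 4 (section 4.1) is to find which measures best reflect improvement, and section 7.2.1 says the sample is meant to inform the power analysis of later studies. Item results that ignore pairing could understate which symptoms respond.

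**Working it through.** The plan gives no power, level or effect size for this test, so there is no figure of its own to reproduce.

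**1. Direction of the error.** Take n pairs with common variance σ² and within-patient correlation ρ. The variance of the difference in means is 2σ²(1 − ρ)/n. An independent-samples test assumes 2σ²/n. The assumed variance is therefore too large by a factor 1/(1 − ρ), which is 2 at ρ = 0.5. Rank tests behave similarly. With ρ > 0 the test rejects too rarely.

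**2. Limiting case by hand.** Baseline scores are 1, 2, 2, 3, 3, 4, 4, 5, 5, 6, and every patient is one point lower at t=8.

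- *Mann-Whitney:* counting pairs with baseline above t=8, and ties as one half, gives U = 2 + 8 + 12 + 16 + 19 + 10 = 67, against an expected 50. The tie sum Σ(t³ − t) is 24 + 60 + 60 + 60 + 24 = 228. The variance is (100/12) × (21 − 228/380) = 170, so the SD is 13.04. Then z = (67 − 50 − 0.5)/13.04 = 1.27 and p = 0.21.
- *Exact signed-rank:* all ten differences have the same sign, so p = 2/2¹⁰ = 0.002.

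Here the correlation is 1 and the change has no spread, so this shows the mechanism, not a typical result.

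**3. Simulation.** Inputs from the plan: ten patients, two visits. Assumptions not in the documents: items scored 0-6; bivariate normal scores rounded and clipped to that range; SD 1 or 1.5; latent baseline mean 1 to 4; correlation 0 to 0.8; shift 0, 0.4 or 0.8 SD; two-sided .05. Low means are included because section 7.1.1 sets a VHI floor of 30 but none for any VTD item. Each setting used 10,000 replicates. Mann-Whitney used the tie-corrected normal approximation. Signed-rank used the exact distribution with zero differences dropped.

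True type I error of Mann-Whitney at nominal 5%:

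| Correlation | 0 | 0.3 | 0.5 | 0.7 |
|---|---|---|---|---|
| Type I error | 4.2-4.5% | 2.0-2.5% | 0.8-1.2% | 0.2-0.3% |

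The exact signed-rank test is also conservative on such coarse scores, at 0.6-3.4%.

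Power for a 0.8 SD shift, Mann-Whitney against signed-rank:

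| Correlation | Mid-scale items (mean 3-4) | Low-scoring items (mean 1) |
|---|---|---|
| 0 | 34-36% v 25-29% | 31% v 18% |
| 0.3 | 32-34% v 31-38% | 28-29% v 21% |
| 0.5 | 30-32% v 38-47% | 27-28% v 25% |
| 0.7 | 28-30% v 52-65% | 24% v 31-32% |

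Items with mean 2 fall between: 29-30% v 36-41% at correlation 0.5. For a 0.4 SD shift at 0.5 both tests are weak: 6-7% v 9-13% mid-scale, and 6% v 6-7% at mean 1. At level .025 with a 0.8 SD shift and correlation 0.5, the figures are 18-19% v 23-30% mid-scale and 16-17% v 12% at mean 1.

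**4. Limit of the paired test.** With m non-zero differences the smallest two-sided exact p is 2/2ᵐ: m = 5 gives .0625, m = 6 gives .031 and m = 7 gives .016. So at least 6 are needed at .05 and 7 at .025. The shares of samples with fewer than 6, at correlation 0.5-0.7, are:

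| Shift | Mean 3-4 | Mean 2 | Mean 1 |
|---|---|---|---|
| 0.8 SD | 4-16% | 9-19% | 38-49% |
| 0.4 SD | about 8-40% | about 13-41% | about 38-64% |

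**The case against.** The best defence is that this hardly matters. It touches item-level results of one secondary outcome in a ten-patient proof-of-concept study. With positive correlation it cannot manufacture a benefit. The replacement is not uniformly better: under the stated assumptions it has less power at correlation 0, and for low-scoring items at 0.3 and 0.5 as well. Every power figure rests on an assumed item range, SD, correlation and shift. Section 5 also describes the .025 level as protecting both primary and secondary outcomes, so a .05 level for the items is a choice and not a correction. Finally, the treatment-session box of the study flow chart allows patients to leave the study, so there may be fewer than ten pairs, and the minimum number of non-zero differences becomes harder to reach.

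All of this stands as a limit on importance, and it means the argument should rest on validity rather than power. None of it makes an independent-samples test suitable for paired scores. Nor does the following sentence on subgroups explain the choice, since it assigns those comparisons to ANOVA.

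**Conclusion.** The point holds and is minor. The named test does not fit the design, and the plan is inconsistent between two adjacent sentences about the same scale. This follows from the text and needs no assumption.

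The size does depend on assumptions. If the within-patient correlation is positive, a nominal 5% test operates at about 2% or less for correlations from 0.5 upwards, and at 2.0-2.5% at 0.3. For a 0.8 SD shift, pairing gains 8-16 points of power at correlation 0.5 for mid-scale items and loses 2-3 points for low-scoring items. At 0.7 the gains are 24-35 and 6-8 points. The VHI analysis and the VTD totals are unaffected.

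**What to change.** The essential change is to replace Mann-Whitney with a paired rank test. Suggested text for section 5, Other Questionnaires:

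> For each VTD item, frequency and severity at t=0 and t=8 will be compared, in patients assessed at both visits, with the Wilcoxon signed-rank test on each patient's t=8 minus t=0 difference (exact p-value allowing for ties, zero differences dropped), at a two-sided level of .05. These item-level results are exploratory, are not adjusted for multiplicity and support no confirmatory claim. The median change and the numbers of patients improved, unchanged and worse will be reported for every item. Items with fewer than 6 non-zero differences, which cannot reach p<.05, will be reported descriptively only.

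If the authors prefer to extend .025 to these tests, change the level and raise the minimum to 7. Either choice is defensible if it is fixed before the data are seen.

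**Cost:** one sentence becomes four, with no extra data or patients. The price is some items without a p-value, often the low-scoring ones, and lower power where the correlation is near zero (6-10 points for mid-scale items and 12-14 for low-scoring items, for a 0.8 SD shift). The counts of patients improved, unchanged and worse remain informative in those cases.

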### **Recording and Analysis of therapy sessions**

Those patients who agree for their therapy sessions to be recorded will have these recordings made using NUH Trust approved software on an NUH Trust laptop/computer together with the other

**CONFIDENTIAL**

Page 20 of 39

IRAS 306954; 19ET004 Protocol V2.1 28 Mar 2022

SHORT TITLE/ACRONYM: CVT4MTD

IRAS:306954

patient data in a secured research database storage area. The anonymised sessional recordings will then be transcribed by a member of the research team and redacted to exclude any personal or identifiable information. In addition, a qualitative assessment of the anonymised therapists' sessional treatment records will be made using a preliminary organising framework and initial codes based on the target of the therapy methods applied during the treatment sessions. These codes will be based on physiological principles, laryngeal setting, treatment methods based on the terms used in the voice therapy and CVT literature and will be coded using the qualitative research management software NVivo based on the principles of Template Analysis (King, 2012), a commonly used thematic analytical framework allowing for a priori and crystallising themes in qualitative analyses. The main aim is to identify the differences and similarities of SLT-VT and CVT-VT approaches to therapy.

## 6. STUDY SETTING

- Single centre study
- Patients will be recruited from the ENT/SLT joint voice clinic at the ENT Department, Queen's Medical Centre Campus, Nottingham University Hospitals.
- In addition, patients with a diagnosis of MTD who are on the waiting list for SLT-VT will be invited to take part in the study.
- Site specific requirements to run the study: The initial and final assessments need to be performed in the research clinic in the ENT Department to allow specialist acoustic, EGG, MPT and videostroboscopic examinations (optional) to take place.
- Therapy treatment sessions will be done using Telehealth through a CVT-P patient video link. Documentation of therapy sessions will be done using standardised proformas (on-line or paper) (based on [Appendix 4](#))

## 7. SAMPLE AND RECRUITMENT

### 7.1. Eligibility Criteria

All patients who meet the inclusion/exclusion criteria and who give consent will be invited to take part. Ten consecutive patients will be recruited. All participants will have a multidisciplinary and multidimensional assessment (see Table 2) and considered for the study if they have a clinical diagnosis of Type I-III MTD based on consensus agreement of the patient by an SLT-V and

SHORT TITLE/ACRONYM: CVT4MTD

IRAS:306954

Laryngologist and meet the study criteria. No participants will be excluded based on race, ethnicity, or gender.

**Table 2 – Diagnosis of MTD (See Appendix A for more details)**

1) The history of the presentation of the condition and its compatible with a Primary MTD diagnosis;
 
2) Presenting vocal symptoms such as hoarseness, change in voice quality, limitations in pitch, loudness, flexibility, and/or stamina of the voice;
 
3) Absence of organic pathology such as structural abnormalities, neurological and inflammatory conditions on endoscopy;
 
4) Auditory-perceptual voice change judgment which include one or more of the following characteristics: variable or abnormal in quality (strained, pressed, creaky, rough, breathy and asthenic voice), have an abnormal habitual pitch with or without a restricted fundamental speaking frequency range or have abnormal loudness and loudness variability during speech;
 
5) The presence of muscle soreness, tenderness or other evidence of hyperfunction in the thyrohyoid or cricothyroid space and/or suprahyoid muscles on physical examination,
 
6) Laryngoscopic findings of laryngeal hyperfunction pattern (MDP Type 1-III).

----------------------------------------------------------------------------------------------------------------------------------------------------------------------------------------------------------------------------------------------------------------------------------------------------------------------------------------------------------------------------------------------------------------------------------------------------------------------------------------------------------------------------------------------------------------------------------------------------------------------------------------------------------------------------------------------------------------------------------------------------------------------------------------------------------------------------------------------------------------------------------------------------------------------------------------------------------------------------------------------------------------------------------------------------------------------

**7.1.1. Inclusion criteria**

**Table 3: Inclusion criteria**

Males & females
 
18 or above
 
Clinical diagnosis of primary MTD based on history and laryngoscopic assessment (Type (I-III) MDT pattern) through joint assessment by a SLT-V and laryngologist
 
Current voice problems, persistent for greater than 2 months
 
Severity of disorder a) VHI ≥ 30 and b) patient wants therapy
 
Patient willingness to undergo treatment
 
Consent to participate in study protocol

----------------------------------------------------------------------------------------------------------------------------------------------------------------------------------------------------------------------------------------------------------------------------------------------------------------------------------------------------------------------------------------------------------------------------------------------------------------

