#### 4.2. Outcome

The main outcome measure is an improvement in the validated Voice Handicap Index self-assessment score following up to six sessions of therapy by an authorised CVT-P in patients with MTD ([Appendix 1](#))

Secondary outcome measures include:

- 1) A questionnaire to evaluate the acceptability of the approach to patients ([Appendix 2](#))
- 2) A questionnaire to evaluate the perceived effectiveness of the therapy from the Therapist's perspective. ([Appendix 3](#))
- 3) Qualitative comparison of the specific techniques used by the CVT-P based on a log of techniques used during the therapy session ([Appendix 4](#)) and qualitative assessment of anonymised, redacted transcripts of therapy sessions in those who have given additional consent
- 4) Comparison of pre- and post-treatment results of:
  - a. a range of simultaneously acquired acoustic and EGG measures made on voice recordings of continuous speech, phrases based on phonetically selected texts and sustained vowels ([Appendix B](#))

- b. psychoacoustic evaluation of the recorded voice samples using the CAPE-V ([Appendix 5](#)) and CVT derived assessment tools ([Appendix 6](#))
  - c. vocal tract discomfort scale – a self-reported rating scale ([Appendix 7](#))
  - d. change in the aerodynamic measure, the Maximum Phonation Time (MPT) ([Appendix 8](#))
- 5) Review of qualitative and quantitative results with recommendations on the feasibility and design of performing a larger RCT. The results will be published in a peer reviewed publication

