### 7.2.1. Size of sample

As this is a proof-of-concept study the sample size of ten patients was selected arbitrarily to generate the necessary results for a power analysis for future studies.

SHORT TITLE/ACRONYM: CVT4MTD

IRAS:306954

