**10.2. Appendix H – Schedule of Procedures**

Procedures	Visits (insert visit numbers as appropriate)				
	Screening Joint Voice Clinic	Research voice clinic (t=0)	Therapy sessions (x6)	Research voice clinic (t=8)	
Identification of eligible patients	x				
Informed consent		x			
Demographics		x			
Medical history		x			
Outcome measures		x		x	
Therapist documentation			x		
Additional questionnaires				x	

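### The plan does not say which VHI score must meet the entry cut-off of 30; if it is the t=0 score, regression to the mean enters the single-arm primary comparison

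*Combined protocol and SAP*

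**What the plan says.** **Entry rule.** Section 7.1.1, Table 3: "Severity of disorder a) VHI ≥ 30 and b) patient wants therapy".

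**Primary outcome and test.** Section 4.2: "The main outcome measure is an improvement in the validated Voice Handicap Index self-assessment score". Section 5, under VHI: "Paired-samples t tests will be applied to the pre-treatment and post-treatment primary outcome measure scores (total VHI score". There is one group and no control. On significance level, Section 5 adds that "the alpha level for all t-test comparisons will also be assessed at .025"; sidedness is not stated.

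**When VHI is measured.** Section 5 says the study data, including the self-assessment questionnaires, "will be collected after recruitment in a research clinic at the beginning of the study (t=0" and again at t=8. Section 7.2 agrees: "The paper questionnaires and forms will be completed by patients during the attendance at the research clinic at (t=0) and (t=8". In Appendix H the row "Outcome measures" is marked at t=0 and t=8 only.

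**When eligibility is judged.** In Appendix H the only row marked at the screening Joint Voice Clinic is the identification of eligible patients. Section 7.3 invites those who meet the criteria, including patients on the therapy waiting list. Section 7.3.2 has patients who meet the criteria receive the leaflet in the voice clinic, then a phone call, then an invitation to the research clinic. It bars study-specific activity before consent, and the flow chart and Appendix H place consent at t=0.

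**Sample size.** Section 7.2.1: "the sample size of ten patients was selected arbitrarily to generate the necessary results for a power analysis for future studies".

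**The concern.** Eligibility is decided before t=0, but the plan schedules no VHI at that point. The diagnostic work-up in Table 2 does not include one, and Section 7.3 does not mention a VHI on file for waiting-list patients. The only pre-treatment VHI the plan documents is the t=0 score. It could therefore be the score that satisfies the cut-off as well as the one entered as the pre-treatment value.

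If so, patients whose score is high by chance on that day get in and those low by chance do not. The group mean is then expected to fall by t=8 even if therapy does nothing. With no control group, the paired t test cannot separate that fall from a treatment effect. The observed change is also what the ten patients are meant to supply for later power calculations, so an inflated change would be carried forward.

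**Working it through.** The sample size of ten has no stated inputs, so there is no figure in the plan to reproduce. The check asks how large the artefact is under each reading of the entry rule.

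**Inputs from the documents:** cut-off 30; n = 10, so 9 degrees of freedom; alpha .025. The test is taken as two-sided, which is an assumption.

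**Inputs assumed, because the documents give none:** unselected clinic VHI mean μ from 30 to 50, SD σ from 20 to 25, test-retest correlation r from 0.7 to 0.9, normal scores, no treatment effect.

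**Formulas when the t=0 score is the qualifier:**

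- z = (30 − μ)/σ and λ = φ(z)/(1 − Φ(z)). The mean of selected patients is μ + σλ.
- Expected spurious improvement = (1 − r) × σ × λ.
- Variance of selected scores = σ²(1 + zλ − λ²).
- SD of change = √[(1 − r)² × that variance + σ²(1 − r²)].
- Rejection rate: non-central t with 9 degrees of freedom and non-centrality (improvement / SD of change) × √10.

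**Worked case, μ = 40, σ = 20, r = 0.8:** z = −0.5 and λ = 0.509, so the selected mean is 40 + 20 × 0.509 = 50.2. Improvement = 0.2 × 20 × 0.509 = 2.04. Selected variance ≈ 194.5. SD of change = √(0.04 × 194.5 + 400 × 0.36) = 12.3.

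| μ | σ | r | Spurious improvement | SD of change | Rejection at .025 | Rejection at .05 |
|---|---|---|---|---|---|---|
| 50 | 20 | 0.9 | 0.58 | 8.9 | 2.7% | 5.4% |
| 50 | 25 | 0.7 | 2.76 | 18.7 | 3.7% | 7.0% |
| 40 | 20 | 0.8 | 2.04 | 12.3 | 4.1% | 7.6% |
| 40 | 25 | 0.7 | 4.21 | 18.6 | 5.5% | 9.9% |
| 30 | 25 | 0.7 | 5.98 | 18.4 | 8.9% | 15.1% |

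The first and last rows are the extremes of the grid. Simulated trials of ten patients agree with these rates to within about 0.1 percentage points. Widening the assumptions to a mean of 60 and r down to 0.6 gives 0.3 to 8.0 points and simulated rejection of about 2.4% to 11.7% at .025.

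The SD of change has to come from the same inputs as the shift. Pairing a 6-point shift with a convenient SD of 15 gives 12.7% at .025 and 20.5% at .05. But the inputs that produce 6 points imply an SD of 18.4, and with that the rates are 8.9% and 15.1%.

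**When a separate earlier score is the qualifier:** with measurement errors independent of the t=0 score, the simulated mean change under no effect is within 0.05 points of zero. Rejection is 2.4-2.7%, which is nominal.

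**The case against.** The strongest reply is that the documents lean towards eligibility being settled before t=0. Appendix H ticks it at the screening clinic, Section 7.3.2 has patients meet the criteria before they are phoned, and Section 5 has data collected after recruitment. The qualifying VHI would then be a routine-care score. A schedule of study procedures would not be expected to list it, particularly as study-specific activity is barred before consent. This stands. A reader might infer from the cut-off and schedule that regression to the mean is definitely built into the primary result. The documents do not support that: they leave the qualifying score unspecified, and on the reading just described the threshold-induced bias largely vanishes.

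A second reply is that the top of the range needs half of clinic patients to score below 30 (a mean of 30), for which the documents offer no evidence. For means of 40 to 50 the rejection rate is 2.7-5.5% at .025. This also stands.

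A third is that this is a ten-patient proof-of-concept study whose t test is not confirmatory, that a larger RCT is still only being assessed for feasibility (Section 4.1), and that a single-arm change does not give the between-arm difference on which an RCT is powered. That limits the consequence but does not remove it, since Section 7.2.1 gives feeding a future power analysis as the reason for recruiting ten patients.

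None of these replies answers the gap itself: the reading that protects the analysis is not written down.

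**Conclusion.** The concern holds in conditional form. VHI is both the entry threshold and the single-arm primary outcome, the only scheduled pre-treatment VHI is at t=0, and the qualifying score is not identified. If the t=0 score does both jobs, the expected spurious improvement is about 0.6 to 6.0 points, with a false-positive rate of about 2.7-8.9% against a nominal 2.5% (about 5.4-15% against 5%). If an earlier score with independent error qualifies patients, the artefact is about zero.

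These figures rest on assumed mean, SD and reliability. The effect is small if most clinic patients score well above 30 and material if many score near it. This should be corrected because the correction is nearly free; it does not invalidate the study.

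**What to change.** State three things in Sections 7.1.1 and 5:

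- The cut-off of 30 is applied to the routine VHI taken at the Joint Voice Clinic or, for waiting-list patients, to the clinic VHI on file.
- A fresh VHI at t=0 is the pre-treatment value in the primary test.
- The cut-off is not re-applied to the t=0 score.

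Show the clinic VHI at screening in Appendix H. Flag any patient whose only pre-treatment VHI is the t=0 score, and repeat the primary analysis without them.

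The change from the clinic score to t=0 should not be presented as untreated drift. The clinic score would itself be truncated at 30, so that change contains the regression to the mean caused by selection.

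The cost is one schedule row, a few sentences and one sensitivity analysis, with no added visit or patients. The downsides are that a clinic VHI must be on record and that the reported effect may be slightly smaller. The change does not remove natural recovery or the effect of the indirect voice therapy that the flow chart gives to every patient at t=0. Both remain mixed with the CVT effect in a single-arm comparison.
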